6.1.5 Dosing and Administration

AMO-01 will be administered as a single dose via intravenous infusions over a 6 hour period, with the total dose administered as 120 mg/m^2 .

6.1.6 Route of Administration

Following dilution of the sterile bulk formulation to final formulation concentration, AMO-01 will be administered intravenously over a 6 hour period.

6.1.7 Starting Dose and Dose Escalation Schedule

Not Applicable

6.1.8 Dose Adjustments/Modifications/Delays

Not Applicable

6.1.9 Duration of Therapy

The expected duration of participation is 12 weeks. Participation for individual subjects will consist of up to 4 weeks of an initial Screening period followed by a Baseline Day 0 visit. At this visit, if the subject is eligible they will receive a single 6-hour intravenous infusion for a total dose administered of 120 mg/m² of AMO-01. Subjects will return for follow-up visits at 1 day and 1, 2 and 4 weeks post-dose. A follow-up phone call will be conducted 8 weeks post-dose.

6.1.10 Tracking of Dose

Not Applicable

6.1.11 Device-Specific Considerations

Not Applicable

6.2 Study Agent Accountability Procedures

In accordance with regulatory requirements, the Investigator or designated site staff must document the amount of IMP received from AMO Pharma. Following receipt they should document the amount of IMP dispensed and/or administered to study subjects and the amount returned to the pharmacy. Product accountability records must be maintained throughout the course of the study.

At the end of the study, all IMP will be reconciled and all remaining materials will be destroyed by the site according to the sponsor's instruction once it has been inventoried and drug accountability records reviewed. All destroyed IMP must have a documented proof of destruction.

7 Study Procedures and Schedule

Refer to Table 1 for an overall schedule of assessments for each visit. Refer to Table 2 for a detailed schedule of assessments to be completed on V2.

7.1 Study Procedures and Evaluations

All assessments will be performed by the investigator or appropriately delegated and trained personnel.

7.1.1 Medical/Surgical and Medication history

The investigator must record all medically and clinical relevant information regardless of the time since the date of diagnosis.

History should include (but is not limited to):

- All current and past non-pharmacologic therapies taken 1 month before the Screening Visit (V1)
- History of respiratory, cardiovascular, renal, gastro-intestinal, hepatic, endocrine, hematological, neurological, psychiatric and any other diseases

7.1.2 Physical Examination

A full physical examination will be conducted. This will be completed by a delegated physician.

A full physical examination is composed of a review of the following body systems:

- General appearance
- Skin
- Head, eyes, ears, nose and throat
- Respiratory
- Cardiovascular
- Abdomen (including liver and kidneys)
- Musculoskeletal
- Neurological

Any abnormalities that are identified at the Screening Visit (V1) will be documented in the subject's source and on the medical/surgical history CRF page. Any changes (including new and worsening findings) between the Screening Visit (V1) and end of study should be captured as AEs on the AE CRF page, as determined by the Investigator.

If an improvement/resolution of a physical examination finding documented in the subject's medical history occurs during the study, it should be recorded in the source document. If there is resolution of a physical examination finding previously noted as an AE, then the event resolution and stop date should be recorded on the AE CRF page.

7.1.3 Height

A calibrated stadiometer should be used to measure height. Height should be measured in centimeters without shoes with the subject standing on a flat surface and with their chin parallel to the floor. The body should be straight but not rigid. The subject's height should be recorded to the nearest 0.5cm.

7.1.4 Weight

The same calibrated scale should be used for all weight measurements for a subject. Weight should be measured in kilograms without shoes and recorded to the nearest 0.1 kg. Bulky items should be removed whenever possible to ensure the most accurate weight is recorded.

7.1.5 Adverse Event collection

Subjects will be questioned in a non-leading way to determine if AEs have occurred since the last visit e.g. "Have you had any health problems since your last visit?" AE's will be collected from the time of consent. Refer to section 8 Safety for additional details of AE collection and reporting.

7.1.6 Vital signs

Vital signs will include the following measures: temperature, pulse, systolic and diastolic blood pressure and respiratory rate. Blood pressure and pulse will be determined after the subject has been in the sitting position for 5 minutes.

Blood pressure should be determined by cuff (using the same method, the same arm, and in the same position throughout the study). A BP cuff appropriate for the subject's arm length and girth should be used for all BP measurements. The cuff should be approximately two-thirds the length/width of the subject's arm (from elbow to shoulder). The cuff should be calibrated and ideally the same cuff should be used on a subject throughout the study. All BP measurements should be performed by the same study site personnel (if possible) throughout the study.

Any vital signs which in the opinion of the investigator are deemed to be clinically significant are to be recorded as an AE. Any clinically significant abnormalities at the last in-clinic study visit (V6) should be followed up and repeated until they have returned to baseline or are, in the opinion of the investigator, no longer clinically significant.

7.1.7 ECG

All the 12 lead ECGs will be performed using a GE MAC 5500 ECG machine. The investigator will perform the interpretation of the ECG immediately after collection to ensure the safety of each subject.

The study site will be required to print out at least 1 copy of the original tracing of the ECG. The original ECG(s) should be signed by the investigator, and maintained at the site with the subject's medical records. The investigator will be responsible for determining the clinical significance of each ECG.

The HR, PR interval, QRS interval, and QT interval will be measured and QTcB and QTcF will be calculated for all ECGs.

Subjects will be assessed in a quiet state (after 5 minutes of rest) in the supine position. A standard ECG recording device will be used with the standard paper rate of 25 mm/second and the standard scale setting of 10 mm/volt.

Three ECGs will be obtained at the Screening Visit (V1) to determine subject eligibility. Subjects will not be eligible for inclusion in this study if they have an abnormal clinically significant ECG at the Screening Visit (V1). The eligibility of a subject will be based on the assessment of the ECG by the investigator, in consultation

with the medical monitor. The investigator will evaluate the potential impact of an abnormal, clinically significant ECG on the continued participation of the subject.

For all other visits, where an ECG is requested according to the schedule of assessments, these will also be performed in triplicate (ideally separated by at least five minutes).

7.1.8 Caregiver-Completed Seizure Diary

A diary will be provided to the subject/caregiver at each visit from Screening (V1) to Week 2 (V5) which should be completed every day. The diary should be returned at each subsequent visit and the diary should be reviewed by a delegated member of the study team. The diary will be collected at Week 4 (V6). The diary should be completed in full so that the following information can be ascertained:

- Date/time of seizure activity
- Length of seizure
- Type of seizure

A copy of the caregiver-completed seizure diary is located in APPENDIX B: Caregiver Completed Seizure Diary.

7.1.9 Syndrome-specific Clinical Global Impressions Improvement Scale (CGI-I)

The clinician administered Clinical Global Impressions of Severity (CGI-S) and Improvement (CGI-I) scale (Guy, 1976) will be performed in accordance with schedule of assessment. The CGI rating scale permits a global evaluation of the subject's improvement over time and will be administered as detailed in the schedule of assessments.

The CGI-S is a 7-point Likert type scale that requires the clinician to rate the severity of the subject's illness at the time of assessment, relative to the clinician's past experience with subjects who have the same diagnosis. Considering total clinical experience, a subject is assessed on severity of illness at the time of rating 1, normal, not at all ill; 2, borderline ill; 3, mildly ill; 4, moderately ill; 5, markedly ill; 6, severely ill; or 7, extremely ill.

The CGI-I requires the clinician to rate how much the subject's illness has improved or worsened relative to a baseline state. A seven point Likert type scale is used from 1 = very much improved, 2 = much improved, 3 = minimally improved, 4 = no change, 5 = minimally worse, 6 = much worse, 7 = very much worse.

CGI-I ratings should be compared against the CGI-S, done at Baseline (V2).

In this study, a standard set of probes/prompts will be provided to the sites to assist the evaluator in eliciting commentary from the subject or their caregiver across each of the core domains of the affected individual's PMS and also on associated symptoms. Every effort will be made so that the same evaluator will also observe the subject at each visit to the clinic.

A copy of the CGI-S and CGI-I to be used in the study, along with instructions is included in APPENDIX C: Syndrome Specific Clinical Global Impressions- Severity and Improvement.

7.1.10 Clinician-completed PMS Domain Specific Causes for Concern Visual Analogue Scale (VAS)

The Clinician-completed PMS Domain Specific Causes for Concern VAS is a 9 item VAS completed by the clinician that scores the severity of concerns in the following domains that are clinically relevant in PMS:

- Speech and language difficulties
- Problems with thinking and learning
- Seizures

Study ID: AMO-01

- Problems with gross motor functioning
- Restricted interests and/or repetitive behaviors
- Social communication problems
- Sensory sensitivities
- Activities of daily living
- Sleep disturbance

For each subject, the clinician is instructed to identify the top 4 or 5 items that are of particular concern and that the clinician would most like to see change during the course of treatment with the study medication. These same 4 or 5 concerns are rated again on each occasion that the clinician completes this assessment measure. The severity of the clinician's concern in each domain is scored by using a 10 cm VAS, with anchors of "not at all severe" at the left end and "very severe" at the right end. The clinician is asked to make a vertical line indicating his/her level of concern in each domain, using a time frame of the past week for reference. A score for each domain is determined by measuring the number of centimeters on the 10-cm VAS line from the anchor point on the left side of the line. A total VAS score for each subject is calculated as the sum of the scores for the 9 domains and is reported as both an absolute number and a percentage of the total possible line length (e.g. xx cm).

The Clinician-completed PMS Domain Specific Causes for Concern VAS will be administered according the schedule of assessments.

A copy of the Clinician-completed PMS Domain Specific Causes for Concern VAS is included in APPENDIX A: Clinician-Completed PMS Domain-Specific Causes for Concern VAS.

7.1.11 Top 3 Caregiver Concerns VAS

The Top 3 concerns VAS allows caregivers to identify their main three causes of concern, related to the subject's PMS, rather than these being pre-specified within a scale, and then rating how these concerns have changed at specific time-points during the study.

Caregivers will be asked to rate each of the three causes for concern by drawing a vertical mark on a 10cm long VAS with anchors of "not at all severe" at the left end and "very severe" at the right end. The 3 concerns related to the subject's PMS will be chosen and rated at baseline. These 3 signs and symptoms will be rated again according to the schedule of assessments using the same scales.

A copy of the Top 3 concerns VAS is included in APPENDIX D: Top 3 Caregiver Concerns VAS.

7.1.12 Aberrant Behavior Checklist (ABC) score

The Aberrant Behavior Checklist (ABC) is a 58-item rating scale to be completed by a caregiver. Five subscales measure the following items: a) irritability (15 items), b) lethargy/social withdrawal (16 items), c) stereotypic behavior (7 items), d) hyperactivity/noncompliance (16 items), and e) inappropriate speech (4 items). A copy of the ABC is included in APPENDIX E: Aberrant Behavior Checklist – Community (ABC).

7.1.13 Repetitive Behavior Scale- Revised (RBS-R) score

The Repetitive Behavior Scale- Revised (RBS-R) is a 44-item caregiver-report questionnaire that is used to measure the breadth of repetitive behavior in children, adolescents and adults with Autism Spectrum Disorders. RBS-R includes six subscales: sterotyped behavior, self-injurious behavior, compulsive behavior, routine behavior, sameness behavior, and restricted behavior. Caregivers will be asked to read a list of behaviors and score on a 4-point likert scale ranging from "0- Behavior does not occur" to "3- Behavior occurs and is a severe problem".

A copy of the RBS-R is included in APPENDIX F: Repetitive Behavior Scale- Revised (RBS-R).

7.1.14 Sensory Assessment for Neurodevelopmental Disorders (SAND)

The SAND is a clinician-administered assessment and corresponding caregiver interview that is not dependent on verbal or cognitive ability and is therefore appropriate for severely affected or nonverbal individuals. The algorithm measures sensory discrete hyperreactivity, hyporeactivity, and sensory-seeking behaviors across visual, tactile, and auditory domains. The SAND has also been validated in ASD with significant correlation to the previously validated Sensory Profile. Results from our preliminary data suggest the SAND can identify sensory reactivity subtypes that differentiate Fragile X syndrome and other forms of ASD.

7.1.15 Follow-up Telephone Call

The follow-up telephone call will be conducted by the study clinician and will address the following questions:

- 1. If applicable, is the participant's seizure activity the same, worse, or better than recorded at Week 4?
- 2. Are there any other clinical changes since Week 4?

7.2 Laboratory Procedures/Evaluations

7.2.1 Clinical Laboratory Evaluation

All clinical laboratory assays will be performed according to the local laboratory's normal procedures. Reference ranges will be supplied by the local laboratory and will be used to assess the laboratory data for clinical significance and out of range changes.

Biochemistry

A biochemistry sample will be collected at screening and each clinic visit. Sample collection will include: sodium; potassium; chloride; carbon dioxide; urea nitrogen; creatinine; glucose; alkaline phosphatase; gamma-glutamyl transferase (GGT); alanine aminotransferase (ALT); asparate aminotransferase (AST); lactate dehydrogenase (LD); bilirubin (total and direct). Biochemistry blood samples should be drawn with the subject in a non-fasting state.

Hematology

A full blood count with differential should be collected at screening and each clinic visit and include: red blood cells; white blood cells (including differential); hemoglobin; hematocrit; platelets.

Urinalysis

Urinalysis will be performed by sending a sample to the local laboratory. Subject/caregiver will collect sample in clean/sterile urine collection cup. If needed, a toilet hat will be used for collection. If necessary, urine may also be collected from a diaper by squeezing urine from the diaper gauze pad directly into collection cup.

Pregnancy Test

A urine or serum pregnancy test for female subjects of child bearing potential will be performed at Screening and at all subsequent clinic visits.

Lipid Panel

A non-fasting lipid panel will be collected at Baseline (V2) and Follow-up (V4) and will include cholesterol; high density lipoprotein (HDL) cholesterol; low density lipoprotein (LDL) cholesterol; triglcyerides; very low density lipoprotein (VLDL) cholesterol.

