Repetitive Behavior Scale- Revised (RBS-R)	Х		
Electroencephalography			
Computerized eye tracking	X		
Auditory Evoked Potential	X		
Visual Evoked Potential	X		X
Adverse Events	X	Х	X
Concomitant Medications	X	Х	X

1. When marked with a) a brief physical examination is acceptable

2. Vital Sign Measures include Heart Rate, Respiratory Rate, Blood Pressure, Temperature. When marked with b) Height, and Weight are also measured

3. ECG during infusion to be completed between 4-6 hours after infusion start

4. Clinical labs standardly include i) Full Blood Count with differential, ii) Biochemistry panel

5. Urine or serum pregnancy test is sufficient

6. Pharmacokinetic sample (6 mL) will be taken pre-infusion and at approximately 2 hours and approximately 6 hours after the start of the infusion as well as 1 hour after the cessation of the study drug.

- 7. 6 mL blood sample required for assessment of phosphorylated ERK levels will be taken pre-infusion and at approximately 2 hours and approximately 6 hours after the start of the infusion as well as 1 hour after the cessation of the study drug.
- 8. A single 6-hour intravenous treatment will be given to subjects, with total dose administered 120 mg/m^2
- 9. Post-infusion assessments will occur one hour after infusion prior to discharge with the exception of EEG which occurs the following day in the AM
- 10. If required for scheduling, pre-infusion assessments can be completed one day prior to the infusion

ii. Table of Contents

i. I	Protocol Synopsis	4
ii.	Table of Contents	14
LIS	ST OF ABBREVIATION	19
iii.	. Table of Tables	20
iv.	SCHEMATIC OF STUDY DESIGN	20
1.	KEY ROLES	21
2.	INTRODUCTION: BACKGROUND INFORMATION AND SCIENTIFIC RATIONALE	23
,	2.1 Background Information	23
	2.1.1 Phelan McDermid Syndrome (PMS)	23
,	2.1.2 AMO-01 and Rationale for Clinical Investigation	23
,	2.1.3 Pre-Clinical Research	25
2.1	1.4 Non-Clinical Pharmacology	25
2.1	1.5 Non-Clinical Pharmacokinetics, Metabolism and Interactions	26
2.1	1.6 Non-Clinical Toxicology	27
2.1	1.7 Clinical Experience	28
2.1	1.8 Safety Summary	28
2.2	2 Rationale	29
2.3	3 Potential Risks and Benefits:	33
3.	OBJECTIVES AND PURPOSE	34
4.	Study Design and Endpoints	34
4	4.1 Description of the Study Design	34
4	4.2 Study Endpoints	35
	4.2.1 Primary Endpoint:	35
	4.2.2 Secondary Endpoints:	35
4	4.2.3 Exploratory Endpoints:	35
5.	Study Enrollment and Withdrawal	36
	5.1 Participant Inclusion Criteria	36
	5.2 Participant Exclusion Criteria	36

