2.1.6 Non-Clinical Toxicology

Studies have been performed in rodents and non-rodents (monkeys) to characterize the toxicity of AMO-01. AMO-01 toxicity was evaluated following single bolus administration in mice, rats, and monkeys and following continuous IV infusion for 7 or 14 days in rat and monkey.

When AMO-01 was administered by continuous infusion for 14 days to cynomolgus monkeys, the NOAEL was 15 mg/kg/day based on reductions in red cell mass at 30 mg/kg/day, and 30 mg/kg/day was considered a nonseverely toxic dose. At the 30 mg/kg/day dose level, effects included: 1) minor clinical signs, including inappetance and unidentified material in the cage pans; 2) a moderate degree of regenerative (reversible) anemia; 3) elevations in serum cholesterol and triglycerides, and a decrease in serum albumin; and 4) diffuse vacuolization of hepatocytes and accumulation of foamy histiocytes (macrophages) in the spleen, which was interpreted to reflect clearance of the hydrophobic components of the vehicle for AMO-01. At the next lowest dose level of 15 mg/kg/day (NOAEL), test article-related anemia and changes in serum chemistry parameters were not observed in the monkeys. No degenerative changes were observed in any organs (including the infusion site), and there were no effects on body weight, ocular condition, electrocardiographic activity or any other parameters assessed in the monkeys. The monkeys used in the 14-day toxicity study were 24 to 31 months of age at start of treatment. This corresponds to ~8 to 10 years of age in humans (Weinbauer et al., 2011) and, therefore, supports the proposed enrolment age of 12 years and above in the planned clinical trial in PMS patients.

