2.3.1 Known Potential Risks

In clinical studies, forty-six patients with solid tumors or GBM have been exposed to AMO-01 at dose levels of up to 480 mg/m²/day for up to 29.6 days. The AEs leading to drug discontinuation that were related to study drug included anaphylactoid shock, clot and fatigue. It is not felt that such AEs would pose significant risk to patients with PMS, and if these or other AEs do occur, it is anticipated that they will resolve readily upon discontinuation of the study drug. Additional information describing the anaphalactoid case is included in the Investigator's Brochure, pp 96-98.

The overall risk profile of AMO-01 has been shown to be acceptable in the clinical studies conducted to date. The unmet need in this population and lack of treatment options supports the investigation of AMO-01 for the treatment of PMS patients with co-morbid epilepsy.

In nonclinical studies, no target organ toxicity was identified. Slight changes in hematology parameters (regenerative anemia) and clinical chemistry parameters (elevations in cholesterol and triglycerides) were observed in monkeys at doses above the dose proposed for the clinical trial in PMS. These effects are easily monitorable and are not anticipated at the proposed clinical dose.

Therefore, the potential benefits outweigh the safety risks of a trial with AMO-01 in PMS patients with comorbid epilepsy.

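### The plan specifies no test for the albumin decrease seen in monkeys, and Table 2 omits the Baseline lipid panel that Table 1 and section 7.2.1 require

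*Combined protocol and SAP*

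**What the plan says.** Section 2.1.6 describes the 14-day monkey infusion study. At 30 mg/kg/day, above the no-effect dose of 15 mg/kg/day, it reports "a moderate degree of regenerative (reversible) anemia" and, in serum chemistry, "elevations in serum cholesterol and triglycerides, and a decrease in serum albumin".

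Section 2.3.1 restates the anemia and the two lipid changes, does not mention albumin, and concludes: "These effects are easily monitorable and are not anticipated at the proposed clinical dose".

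Section 7.2.1 itemises the tests. The biochemistry list has five entries from sodium to urea nitrogen, followed by "creatinine; glucose; alkaline phosphatase; gamma-glutamyl transferase (GGT); alanine aminotransferase (ALT); asparate aminotransferase (AST); lactate dehydrogenase (LD); bilirubin (total and direct". The hematology list covers red cells, hemoglobin and hematocrit. On lipids: "A non-fasting lipid panel will be collected at Baseline (V2) and Follow-up (V4".

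Table 1 agrees on the lipid timing. Its Clinical Labs row carries the lipid mark at V2 and V4 and at no other visit. For the Baseline visit, footnote 8 of Table 1 and section 7.3.2 both refer to Table 2, and the opening of section 7 says: "Refer to Table 2 for a detailed schedule of assessments to be completed on V2". Footnote 4 of Table 2 reads "Clinical labs standardly include i) Full Blood Count with differential, ii) Biochemistry panel" and has no lipid clause.

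Section 4.2.1 makes the incidence of abnormal laboratory values part of the primary endpoint.

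**The concern.** This is a single-arm study of up to 10 treated subjects, so each subject's own pre-dose value is the only comparator for a laboratory change. Section 10.1 takes baseline as the last measurement before study drug, and section 10.4.1 subtracts it from later values. A pre-dose value that was not drawn cannot be recovered after the infusion.

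Two things are at stake. An effect that the sponsor's own toxicology identified may go unmeasured because no analyte is specified for it. For two further effects, the instructions for the visit that supplies the baseline disagree. In either case a report of no albumin or lipid signal could reflect missing data rather than absence of an effect.

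**Working it through.** The plan states no figure to reproduce. The check sets the toxicology findings against the specified tests and then compares the schedules.

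**Step 1. Effects against tests**

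| Effect in monkeys (2.1.6) | Restated in 2.3.1 | Test specified in 7.2.1 |
|---|---|---|
| Anemia | Yes | Yes, blood count |
| Cholesterol up | Yes | Yes, lipid panel at V2 and V4 |
| Triglycerides up | Yes | Yes, lipid panel at V2 and V4 |
| Albumin down | No | None |

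The biochemistry list has 5 + 8 = 13 entries. None is albumin or total protein. So 3 of the 4 effects have a specified test and 1 does not.

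**Step 2. Lipid schedule, source by source**

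| Source | V1 | V2 | V4 | V5 | V6 |
|---|---|---|---|---|---|
| Clinical labs drawn (Table 1) | Yes | Yes | Yes | Yes | Yes |
| Lipids, Table 1 | No | Yes | Yes | No | No |
| Lipids, section 7.2.1 | No | Yes | Yes | No | No |
| Lipids, Table 2 (V2 only) | – | Not listed | – | – | – |

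The mark that means a lipid panel in Table 1 means a brief physical examination in Table 2. It does not appear on Table 2's Clinical Labs row, so nothing there signals the extra test.

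**Step 3. Consequence**

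- V2 run from Table 1 or section 7.2.1: one pre-dose and one post-dose lipid panel, so change = V4 − V2 can be computed.
- V2 run from Table 2 alone: no pre-dose panel, because V1 has none either. V4 can be read against the reference range, but a new abnormality cannot be told from a pre-existing one, and no change can be computed.
- Lipid panels scheduled after Week 1: 0, although clinical labs are drawn at V5 and V6.

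**Step 4. Exposure context (Table 3)**

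- Sustained concentration, planned over monkey no-effect dose: 2732 / 1173 = 2.33, so planned is higher.
- Tabulated AUC, monkey no-effect dose over planned: 400,116 / 217,500 = 1.84, so planned is lower.
- Concentration times infusion time, ignoring the tail after infusion: 2732 × 6 = 16,392 ng·h/mL, and 400,116 / 16,392 = 24.4, so planned is lower still.

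The direction depends on the exposure measure. The gaps in steps 1 to 3 do not depend on it.

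**The case against.** Several stronger readings are tempting, and the documents do not support them.

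- *The effects called easily monitorable are not monitored.* In section 2.3.1 that phrase refers to anemia, cholesterol and triglycerides, and each has a planned test. The point is that section 2.3.1 leaves albumin out.
- *Albumin will never be measured.* Section 7.2.1 says what collection will include and leaves assays to each local laboratory's usual procedures. A local panel may contain albumin. It is unspecified, and with two sites its availability may differ.
- *The plan drops the Baseline lipid panel.* Two of the three sources require it. Nothing states that Table 2 takes precedence, and its footnote does not exclude other tests. This is an inconsistency; a lost baseline is a possible result of it.
- *A raised Week 1 lipid is never repeated.* Unplanned visits are permitted (7.3.6), the outcome of each adverse event is to be established (8.3), and a grade 3 or higher laboratory abnormality is a halting criterion for the subject (8.5). The accurate statement is that no repeat is scheduled.
- *Laboratory values need the rule that vital signs have.* Section 7.1.6 says clinically significant vital signs at V6 "should be followed up and repeated until they have returned to baseline" or cease to be clinically significant. The absence of a laboratory counterpart contradicts nothing, and whether to add one is a clinical-management decision outside this point.
- *There is no exposure margin.* That holds on concentration only; on both AUC calculations planned exposure is below the monkey no-effect level. Sections 2.1.8.1 and 2.1.8.2 also report unremarkable or minimal laboratory changes in patients at up to 480 mg/m²/day, though neither summary names albumin or lipids.

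What remains is that the written plan specifies no albumin test, that the V2 instructions disagree, and that no lipid panel is scheduled after Week 1. Nothing in the documents explains the albumin omission.

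**Conclusion.** The point holds in this limited form. One of four laboratory effects reported in monkeys has no specified test and is missing from the risk section. For two others, the only scheduled pre-dose measurement depends on which schedule a site follows at V2. Lipids have one scheduled post-dose value and no scheduled recovery value.

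The size is modest. It does not show that subjects are at risk or that the effects are likely at this dose. It affects whether part of a primary safety endpoint can be interpreted. The lipid consequence assumes that a site works from Table 2 alone. The albumin consequence assumes that local panels do not already report it. The documents do not settle either assumption.

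**What to change.** 1. Reconcile Table 2 with Table 1 and section 7.2.1 by adding the lipid panel to the pre-infusion Clinical Labs entry and its footnote. This adds no test beyond what Table 1 already plans.
2. Add serum albumin to the biochemistry list in section 7.2.1, run on samples already drawn, and name the albumin decrease in section 2.3.1. With about 15 subjects screened and up to 10 treated, this is about 15 + (4 × 10) = 55 albumin results on Table 1's schedule.
3. Optionally, run the lipid panel on the V5 and V6 samples to give a recovery value: at most 2 × 10 = 20 further panels.

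The cost is a few lines of text and a small local laboratory charge. No additional visits are needed, and no dose or treatment rule changes.
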